### 3.2 Efficacy Endpoints

The primary efficacy endpoints are:

- Time to sustained resolution of COVID-19 signs and symptoms (in all subjects) as measured by the time from baseline (in hours) when cough, sore throat, nasal congestion, headache, chills and or sweats, myalgia, fatigue, and nausea (with or without vomiting) have been assessed by the subject as none (0) or mild (1) and all symptoms remain at or below 1 until the Day 14 visit. Subjects reporting a persistent fever (100.5 degrees for 36 hours or more) and/or SpO2 levels <96% with any shortness of breath are considered not to have met the success criterion on that day even if all other symptoms are reported as none (0) or mild (1).
- Time to sustained resolution of COVID-19 signs and symptoms (in subjects with mild disease at baseline) as measured by the time from baseline (in hours) when cough, sore throat, nasal congestion, headache, chills and or sweats, myalgia, fatigue, and nausea (with or without vomiting) have been assessed by the subject as none (0) or mild (1) and all symptoms remain at or below 1 until the Day 14 visit. Subjects reporting a persistent fever (100.5 degrees for 36 hours or more) and/or SpO2 levels <96% with any shortness of breath are considered not to have met the success criterion on that day even if all other symptoms are reported as none (0) or mild (1).

Note: The second primary endpoint is defined in the same way as the first primary endpoint, but is evaluated only in subjects with mild disease at baseline.

Secondary clinical endpoints:

- Proportion of study subjects who achieve 'Composite Resolution' at Day 8 defined as both a negative SARS-CoV-2 antigen test within the window for Visit 4 (Days 7 – 9) and all eight symptoms assessed by the subject as none (0) or mild (1), absence of fever and SpO2  $\geq 96\%$  without shortness of breath at study day 8 (as reported on the Diary Card Day 8-Assessment 1).
- Proportion of study subjects who experience progression of COVID-19 as defined by an increase of the composite COVID-19 severity score greater than baseline at any point in the study on or after Day 3.
- Proportion of study subjects who answer yes to either of the following patient-reported global impression assessments independently at each of the Day 8 and Day 14 visits,
  - a) In the past 24 hours, have you returned to your usual health (before your COVID-19 illness)?

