## 5.2 Handling of Missing Data and Data Handling Rules

### 5.2.1 Missing Efficacy Endpoints

In general, missing data will not be imputed with the exception that for the missing viral load results post baseline (nasopharyngeal and saliva biospecimens) will be imputed using the multiple imputation (MI) methodology as described in Section 5.5.2.

For derivation of resolution of COVID-19 symptoms, scenarios of missing diary data (8 symptoms: cough, sore throat, nasal congestion, headache, chills and or sweats, myalgia, fatigue, nausea) in conjunction with vital signs of fever, SpO2 levels, and shortness of breath will be handled as follows:

- Scenario 1: For Day x assessment y (am or pm) with missing severity for some among the 8 symptom(s), if there is at least one symptom scored 2 (moderate) or 3 (severe), subject will be considered failure for Day x assessment y.
- Scenario 2: For Day x assessment y with missing severity for some among the 8 symptom(s), if all non-missing values are 0 or 1, any other symptoms left blank on Day x assessment y will be considered with severity of 0 (none) for the purposes of derivation of resolution of COVID-19 symptoms. Subject's success or failure for Day x assessment y will then be determined by the vital sign data on fever and/or SpO2 level/shortness of breath as follows:
  - If fever of  $\geq 100.5$  and is persistent for  $\geq 36$  hours or SpO2 levels  $< 96\%$  with shortness of breath, the subject will be considered a failure.
  - If SpO2 levels  $< 96\%$  and data is missing for shortness of breath, the subject will be considered a failure.
  - If SpO2 levels  $\geq 96\%$  and data is missing for shortness of breath, the subject will be considered a success.
  - If shortness of breath is "Yes" and SpO2 levels are missing, the subject will be considered a failure.

- If shortness of breath is “No”, and SpO2 levels are missing, the subject will be considered a success.
- If temperature data is missing, the subject will be considered a success if fever was <100.5 on the previous assessment and a failure if the previous two assessments were both ≥100.5.

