- Scenario 3: For Day x (pm), if severity is missing for all 8 symptoms, the diary entries from the previous completed entry, either Day x (am) or Day x-1 (pm), will be carried forward for Day x (pm). For Day x (am), if severity is missing for all 8 symptoms, the diary entries from the previous completed entry, either Day x-1 (pm) or Day x-1 (am) will be carried forward for Day x (am). Same applied to fever and SpO2 level/shortness of breath.
- Scenario 4: For Day x assessment y where all 8 symptoms are scored 0 or 1, if fever or SpO2 level is missing, subject’s success or failure for Day x assessment y will be determined in the same way as in Scenario 2.

For derivation of the primary efficacy endpoints, subjects who were hospitalized due to COVID-19 will be designated as treatment failures, and right censored at 384 hours (16 days), i.e., censored at the end of the Visit 5 window.

For subjects who discontinued the study early for any reason other than hospitalization for COVID-19, only diary data up to subject’s discontinuation date will be used. For derivation of the primary efficacy endpoints such subjects will be considered censored at the time of their last assessment.

**Note:** Subjects discontinuing for any reason are ineligible to meet the success criteria on either primary efficacy endpoint because "success" requires the conditions to be met until the Day 14 visit.

The COVID-19 Composite Severity Score (CSS) at baseline is defined as the sum of the eight individual COVID-19 signs and symptoms severity scores divided by eight. For purposes of calculating the COVID-19 composite severity score in the secondary endpoint of worsening disease from baseline, subjects with missing diary card entries (reporting none of eight symptoms scored) will not be considered to have met the criteria for worsening of disease at that assessment timepoint. Subjects with incomplete diary card entries (reporting from 1 to 7 of the eight symptoms scored), will be handled by dividing the sum of all scores reported by the number of scores reported, and compared to the baseline CSS.

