	-- n (%) subjects who require hospitalization for severe COVID-19	XX (XX.X)	XX (XX.X)	XX (XX.X)	XX (XX.X)
	-- n (%) subjects who require endotracheal ventilation or ECMO	XX (XX.X)	XX (XX.X)	XX (XX.X)	XX (XX.X)
	-- n (%) subjects who die	XX (XX.X)	XX (XX.X)	XX (XX.X)	XX (XX.X)
Modified Full Analysis Set					
	N	XX	XX	XX	XX
	n (%) Subjects who experience progression of COVID-19 	XX (XX.X)	XX (XX.X)	XX (XX.X)	XX (XX.X)
	n (%) Subjects with severe clinical outcomes (at least one of following)	XX (XX.X)	XX (XX.X)	XX (XX.X)	XX (XX.X)
	-- n (%) subjects who require medical attention or intervention attributed to COVID-19	XX (XX.X)	XX (XX.X)	XX (XX.X)	XX (XX.X)
	-- n (%) subjects who progress to severe disease 	XX (XX.X)	XX (XX.X)	XX (XX.X)	XX (XX.X)
	-- n (%) subjects who require hospitalization for severe COVID-19	XX (XX.X)	XX (XX.X)	XX (XX.X)	XX (XX.X)
	-- n (%) subjects who require endotracheal ventilation or ECMO	XX (XX.X)	XX (XX.X)	XX (XX.X)	XX (XX.X)
	-- n (%) subjects who die	XX (XX.X)	XX (XX.X)	XX (XX.X)	XX (XX.X)
Per Protocol Population					
	N	XX	XX	XX	XX
	n (%) Subjects who experience progression of COVID-19 	XX (XX.X)	XX (XX.X)	XX (XX.X)	XX (XX.X)
	n (%) Subjects with severe clinical outcomes (at least one of following)	XX (XX.X)	XX (XX.X)	XX (XX.X)	XX (XX.X)
	-- n (%) subjects who require medical attention or intervention attributed to COVID-19	XX (XX.X)	XX (XX.X)	XX (XX.X)	XX (XX.X)
	-- n (%) subjects who progress to severe disease 	XX (XX.X)	XX (XX.X)	XX (XX.X)	XX (XX.X)
	-- n (%) subjects who require hospitalization for severe COVID-19	XX (XX.X)	XX (XX.X)	XX (XX.X)	XX (XX.X)
	-- n (%) subjects who require endotracheal ventilation or ECMO	XX (XX.X)	XX (XX.X)	XX (XX.X)	XX (XX.X)
	-- n (%) subjects who die	XX (XX.X)	XX (XX.X)	XX (XX.X)	XX (XX.X)

[1]: Progression of COVID-19 is defined by increase of composite COVID-19 severity score (> baseline score) at any point in the study on or after Day 3.

[2]: Subjects will be designated as Severe having any one of the following: Respiratory Rate  $\geq 30$ , Heart Rate  $\geq 125$ , SpO2  $\leq 93\%$ , or lung infiltrates upon imaging  $>50\%$ .

EmitBio Inc.  
Protocol: EB-P20-01  
SAP Version: 2.0

Source: Listing 16.x.x  
O:\Studies\EmitBio\EB-P20-01\Biometrics\Programs\Tables\xxx.sas ran on Month Day, Year at hh:mm on data from Month Day, Year.

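### In the worsening endpoint, a subject whose diary stops at COVID-19 hospitalisation or death is scored as not progressed unless an entry from Day 3 onward already exceeded baseline

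*SAP*

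**What the plan says.** SAP 3.2 defines progression as "an increase of the composite COVID-19 severity score greater than baseline at any point in the study on or after Day 3". Footnote 1 to Table 14.2.2.3 repeats this definition. Neither place mentions hospitalisation or death.

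SAP 5.2.1 gives two missing-data rules for this endpoint:

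- A subject with an entry in which none of the eight symptoms is scored "will not be considered to have met the criteria for worsening of disease at that assessment timepoint".
- An entry with one to seven symptoms scored "will be handled by dividing the sum of all scores reported by the number of scores reported, and compared to the baseline CSS".

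The same section has other rules that might have rescued the case, but their scope excludes it:

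- The hospitalisation rule reads "For derivation of the primary efficacy endpoints, subjects who were hospitalized due to COVID-19 will be designated as treatment failures". It does not reach the secondary endpoints.
- The four diary scenarios, including carry-forward, are introduced with "For derivation of resolution of COVID-19 symptoms, scenarios of missing diary data". They concern resolution, not worsening.
- The general rule begins "In general, missing data will not be imputed with the exception that for the missing viral load results post baseline". Diary scores are not in that exception.

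Hospitalisation and death are components of a separate secondary endpoint, severe clinical outcomes (SAP 3.2). Its rows sit directly below the progression row in Table 14.2.2.3.

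**The concern.** A diary that goes blank at admission is not missing at random: the reason for the gap can be the very worsening that the endpoint is named for. For those entries the rule assigns the favourable value.

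This differs from how the SAP treats missing data elsewhere. A missing nasopharyngeal swab is a failure for viral clearance (SAP 5.5.2). A missing antigen test is a failure for Composite Resolution (Table 14.2.2.1, Note 2). COVID-19 hospitalisation is a failure for the primary endpoints. Protocol 9.2 introduces the worsening measure under severe COVID-19 clinical outcomes, in a paragraph about rapid deterioration or hospitalisation.

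At stake is the credibility of one row. It would understate progression most in the arm with more such admissions or deaths, and it could contradict the hospitalisation row printed just below it.

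**Working it through.** The documents state no rate, sample size or power for this endpoint, so there is no figure to reproduce. The check has two parts.

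**1. Applying the rule to test diaries.** An event is any assessment on or after Day 3 with composite score above baseline. A wholly blank entry is not an event, and a partial entry uses the mean of the reported scores. All three diaries are invented.

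- Baseline scores 2, 2, 1, 1, 1, 1, 2, 0: sum 10, so 10/8 = 1.25.
- Raised scores 3, 3, 2, 2, 2, 2, 3, 1: sum 18, so 18/8 = 2.25.

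| Diary | Result under the SAP |
|---|---|
| Score 2.25 on Day 2, admitted Day 2, blank afterwards | Not progressed: scores before Day 3 do not count |
| Score 1.25 on Days 2–4, admitted Day 5, blank afterwards | Not progressed |
| Score 1.25 on Days 2–3, 2.25 on Day 4, admitted Day 5, blank afterwards | Progressed |

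The problem arises in the first two cases and not in the third. The second is plausible. SAP 3.2 defines severe illness by respiratory rate, heart rate, oxygenation or lung infiltrates, and none of these enters the eight-symptom score.

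Table 14.2.2.3 uses one N per population. Tables 14.2.2.1 and 14.2.2.2 instead use the number of subjects at the visit. Subjects with blank entries therefore appear to stay in the denominator as non-progressors.

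**2. Size per subject and per arm.**

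- Final Cohort up to 180 (SAP 3.3), randomised 2:1: 180 × 2/3 = 120 RD-X19 and 60 sham.
- Table 14.2.2.3 has a pooled sham column and no Final Cohort sham column. Adding the 10 planned Cohort A sham subjects gives 60 + 10 = 70.
- One affected subject: 1/120 = 0.8 points in RD-X19; 1/70 = 1.4 points in pooled sham.

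Let h be the proportion hospitalised or dead from COVID-19, and q the share of those with no recorded rise from Day 3 onward and no later diary. The undercount in an arm is h × q. Both are assumptions:

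| h | q = 25% | q = 50% | q = 100% |
|---|---|---|---|
| 1% | 0.25 points | 0.5 | 1 |
| 3% | 0.75 | 1.5 | 3 |
| 5% | 1.25 | 2.5 | 5 |
| 10% | 2.5 | 5 | 10 |

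In subjects, the extremes are 120 × 0.0025 = 0.3 to 120 × 0.10 = 12 in RD-X19, and 70 × 0.0025 = 0.2 to 70 × 0.10 = 7 in pooled sham. The difference between columns is distorted only when h × q differs between them; equal values cancel.

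**The case against.** **A reader might infer that every subject whose diary stops at hospitalisation or death is scored as not progressed.** The documents do not support that. The blank-entry rule works one assessment at a time and the endpoint can be met at any time from Day 3, so a single earlier raised score keeps the subject as progressed.

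**A reader might also infer that a real difference in hospitalisation would be hidden.** It would not. Severe clinical outcomes are tabulated item by item and as any one or more, in the same table, for the same populations and columns.

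**Diary loss at admission is not certain.** Protocol 9.2 stops device treatment on admission, but Protocol 8.5.4 says that stopping the device is not leaving the study. This stands as a caution on q. However, SAP 5.5.1 itself provides for subjects who leave the study early because of COVID-19 hospitalisation, so the loss is foreseeable.

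**A symptom-score endpoint beside a separate severe-outcomes endpoint is a legitimate design.** The gap also comes as much from the score-only definition as from the blank-entry rule, and the primary-endpoint rule concerns a different outcome, so there is no formal contradiction. All of this stands. It does not explain why a gap caused by hospitalisation should count as evidence of no progression in a row titled progression of COVID-19.

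**The consequence is limited.** Secondary endpoints are descriptive (Protocol 10.4.1, SAP 5.5.2), and hypothesis testing is confined to the two primary endpoints (Protocol 10.1). This stands in full.

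**Conclusion.** The concern holds in a narrow form. A subject hospitalised or dying with COVID-19, with no score above baseline recorded from Day 3 onward and no diary thereafter, is counted as a non-progressor, and no SAP rule overrides this.

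Each such subject lowers the row by about 0.8 points in Final Cohort RD-X19 or 1.4 points in pooled sham, on planned sizes of about 120 and 70. The 0.25–10 point range per arm rests wholly on the assumed h of 1–10% and q of 25–100%. The documents supply neither.

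No primary endpoint, significance level or power figure is touched, and the events remain visible under severe clinical outcomes. The point is still worth correcting: the rule resolves informative missingness in the favourable direction, and the remedy is cheap.

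**What to change.** In SAP 5.2.1, SAP 3.2 and footnote 1 to Table 14.2.2.3, state that COVID-19 hospitalisation or death counts as progression regardless of diary completion. At minimum, keep the diary-only row and add a sensitivity row on this basis beside it. In either case, report by column how many such subjects have no diary data after the event. Leave the handling of other missing cards as planned. Make the change before unblinding.

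Do not bring progression to severe disease into the definition yet. Its criteria differ between Protocol 6.4, Protocol 9.2, SAP 3.2 and footnote 2 to Table 14.2.2.3 (for example, on the respiratory-rate boundary, heart rate and PaO2/FiO2). Those passages must be reconciled first.

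The cost is a short SAP edit and a matching edit to the protocol's definition of worsening. No new data are needed: SAP 3.1 has hospitalised subjects tracked to discharge or death with dates and times, and the hospitalisation and medical-encounter listings are already planned. The downside is that hospitalisation and death would count in both the progression and the severe-outcome rows. The sensitivity-row option leaves the diary-only figure intact.

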## 5.2.2 Missing or Incomplete Dates for Adverse Events and Concomitant Medications

### Adverse Events

Handling of partial dates is only considered for the start date. An adverse event with a partial start date is considered treatment emergent if:

- only the day is missing and the start month/year is the same or after the month/year of the first treatment
- the day and month are missing and the start year is the same or greater than the year of the first treatment date
- the start date is completely missing

### Concomitant Medications

Handling of partial dates is only considered for the stop date. A medication with a partial stop date is considered concomitant if:

- only the day is missing and the stop month/year is the same or after the month/year of the first treatment
- the day and month are missing and the stop year is the same or greater than the year of the first treatment date
- the stop date is completely missing or the medication is ongoing.

### 5.3 Demographics and Baseline Characteristics

Demographics and baseline characteristics will be summarized descriptively for the Safety population.

### 5.4 Subject Accountability

A summary of subject disposition will be provided for all subjects descriptively, including reason for discontinuation and analysis populations.

### 5.5 Efficacy Analyses

The primary analysis population for all primary and secondary efficacy endpoints is the FAS population. Supportive analyses will be carried out on the mFAS and PP populations for the primary endpoints and for all secondary endpoints.

#### 5.5.1 Analysis of Primary Efficacy Endpoint

The primary analysis for each of the two primary endpoints will be the comparison via an unstratified log-rank test between the RD-X19 treatment arm and sham from the Final Cohort and is based on the FAS population. This analysis will be supplemented with a graphical display and medians derived by the Kaplan Meier method.

All time-to-event analyses will be measured starting from the time of randomization. The data handling rules as described in Section 5.2.1 will be applied before analyses of the primary efficacy endpoints. These data handling rules cover cases related to subjects discontinuing the study early due to hospitalization for COVID-19, and cases related to subjects discontinuing the study early due to other reasons. Subjects that did not discontinue early but who did not achieve sustained resolution will be censored at the date of their Visit 5.

The Kaplan-Meier derived medians will be presented from the FAS population for the Final Cohort together with 95% CIs using the Brookmeyer & Crowley (1982) method and will include values for the RD-X19 treatment arm and the Sham arm. 25th and 75th percentiles will also be provided together with their 95% CIs using this same method.

Cox proportional hazards regression models (with a single term for treatment) will be employed to analyze the primary efficacy endpoints to derive a hazard ratio in each case between the RD-X19 treatment arm and the sham arm from the Final Cohort and will be based on the FAS population. Two-sided 95% confidence intervals and two-sided 90% confidence intervals will also be derived for the hazard ratios from the above models.

In addition, to evaluate the potential impact of subject baseline characteristics to the treatment effect estimation, the Cox proportional hazards regression will be performed for the Final Cohort based on the FAS population adjusting for the following set of covariates:

- 1) the COVID-19 Composite Severity Score at baseline defined as the sum of the eight individual COVID-19 signs and symptoms severity scores divided by eight (grouping of <1.25,  $\geq 1.25$ )
- 2) baseline disease status of mild vs. moderate disease (subjects meeting entry criteria are considered to be mild unless the physical/vital signs examination documents clinical signs suggestive of moderate illness)  
All subjects are designated as Mild with the exception of subjects:
  - Who have RR  $\geq 20$  at Baseline
  - Who report Shortness of Breath at Baseline, or
  - Who have clinical signs suggestive of lower airway involvement.
- 3) gender
- 4) age (grouping of <50,  $\geq 50$ )
- 5) baseline antibody status (positive, negative)

Note: For the second primary efficacy endpoint the term for baseline disease status of mild vs. moderate will not be included.

Two-sided 95% confidence intervals and two-sided 90% confidence intervals will also be derived for the hazard ratios from the above models.

Supportive analyses in each case for the two primary efficacy endpoints will be produced for the mFAS and the Per Protocol population. For the mFAS population the Cox proportional hazards regression model will not include the covariate related to baseline antibody status.

All of the above analyses of the primary endpoints will also be produced for pooled RD-X19 doses vs. pooled Sham, and for RD-X19 low dose (i.e., the dose not expanded to produce the Final Cohort) vs. Pooled Sham, but where in all cases these p-values will be viewed as descriptive only. For the analyses of pooled RD-X19 vs. pooled Sham the log-rank test and the Cox proportional hazards models will each be stratified by cohort.

Following notations are used in the sample SAS code:

- TRT: treatment group with values 1 for RD-X19 from Final Cohort, 2 for RD-X19 from Cohort A, and 3 for Sham from Final Cohort, 4 for Sham from Cohort A
- TRTpooL: value 12 for pooled RD-X19 from both cohorts, 3 for pooled Sham
- COHORT: A for first cohort, B for Final cohort
- HOURS: time to sustained resolution of COVID-19 signs and symptoms
- CNSR: the censoring variables, 1 for censored, 0 for not censored
- COVIDSEV: grouping of COVID-19 Composite Severity Score at baseline, 1 for score <1.25, 2 for score  $\geq 1.25$
- DSSTATUS: baseline disease status, 1 for mild, 2 for moderate
- SEX: 1 for males, 2 for females
- AGEGRP: grouping of age, 1 for age <50, 2 for age  $\geq 50$
- ANTIBODY: grouping of baseline antibody status, 1 for positive, 2 for negative

Sample SAS Code for Main Analysis

1. Unstratified analysis of Primary Endpoint 1: Time to sustained resolution of COVID-19 signs and symptoms (in mild and moderate subjects)

a) RD-X19 from Final Cohort vs Sham from Final Cohort, log-rank test (unstratified)

```
PROC LIFETEST DATA=datain CONFTYPE=LINEAR;  
  WHERE trt in (1,3);  
  TIME hours*cnsr(1);  
  STRATA trt/ TEST=LOGRANK;  
RUN;
```

b) RD-X19 from Final Cohort vs Sham from Final Cohort, Cox proportional hazards regression model (unstratified)

```
PROC PHREG DATA=datain;  
  WHERE trt in (1,3);  
  CLASS trt(ref='3') / PARAM=ref;  
  MODEL hours*cnsr(1) = trt /RL;  
  HAZARDRATIO trt / ALPHA=0.05;  
  HAZARDRATIO trt / ALPHA=0.10;  
RUN;
```

c) RD-X19 from Final Cohort vs Sham from Final Cohort, Cox proportional hazards regression model adjusting for pre-specified covariates

```
PROC PHREG DATA = datain;  
  WHERE trt in (1,3);  
  CLASS trt(ref='3') / PARAM=ref;  
  MODEL hours*cnsr(1) = trt COVIDSEV DSSTATUS SEX AGEGRP  
  ANTIBODY /RL;  
  HAZARDRATIO trt / ALPHA=0.05;  
  HAZARDRATIO trt / ALPHA=0.10;  
RUN;
```

Note: For mFAS analysis, variable ANTIBODY is not included as a covariate.

2. Unstratified analysis of Primary Endpoint 2: Time to sustained resolution of COVID-19 signs and symptoms (in mild subjects)

Same SAS code for Primary Endpoint 1 will be used for Primary Endpoint 2 with two changes: (i) the WHERE statement in each case will now include 'and DSSTATUS=1'; and (ii) for analysis c) of Primary Endpoint 2, the variable DSSTATUS is not included as a covariate.

3. For graphical display of survival function by the Kaplan-Meier method:

RD-X19 from Final Cohort vs Sham from Final Cohort  

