3. BMI <40
4. Provides written informed consent prior to initiation of any study procedures.
5. Be able to understand and agrees to comply with planned study procedures and be available for all study visits.
6. Agrees to the collection of saliva, nasopharyngeal, and venous blood specimens per protocol.
7. Males or females, 18 to 65 years of age, inclusive.
8. No uncontrolled disease process(es) based on patient reported medical history (chronic or acute), other than direct COVID-19 signs and symptoms.
9. No physical or mental conditions or attributes at the time of screening, which in the opinion

of the PI, will prevent full adherence to, and completion of, the protocol.

*Symptom scoring is independent from the classification of COVID-19 disease severity at baseline. Guidance to study subjects for grading of signs and symptoms will be based on definitions used for the grading of TEAEs:

- None (Grade 0): Not present
- Mild (Grade 1): Symptoms that are usually transient and may require only minimal or no palliative or specific therapeutic intervention and generally do not interfere with the subject's usual activities of daily living.
- Moderate (Grade 2): Symptoms that are usually alleviated with palliative or specific therapeutic intervention. The symptoms interfere with usual activities of daily living causing discomfort but pose no significant or permanent risk of harm to the study subject.
- Severe (Grade 3): Events interrupt usual activities of daily living, or significantly effect clinical status, or may require intensive therapeutic intervention. Severe events are usually incapacitating.

A subject who meets any of the following criteria will be **excluded** from participation in this study:

1. Positive urine pregnancy test at screening or females who intend to become pregnant during the study.
2. COVID-19 signs associated with severe respiratory distress or imminent serious medical outcomes.^{^^}

^{^^}Potential Study Subjects Presenting with any of the following should be referred for immediate medical care and are not eligible for the study

- Fever > 104° F
- Cough with sputum production
- Rales and/or rhonchi
- Difficulty breathing with respiratory distress defined by a respiratory rate ≥ 30 per minute, heart rate ≥ 125 per minute, SpO₂ $\leq 93\%$ on room air at sea level or PaO₂/FiO₂ < 300 .
- Persistent pain or pressure in the chest
- Confusion

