Subjects who test positive for SARS-CoV-2 antibodies from blood draws at baseline will continue treatment for the duration of the study, undergo all assessments, and be excluded from the modified full analysis set (mFAS). For each subject testing positive for SARS-CoV-2 antibodies at baseline, one additional subject will be enrolled and randomized into the study for each of Cohorts A and B (*does not apply to optional enrollment period once the dose has been selected for the additional 150 subjects).

Safety and tolerability (local reactogenicity) will be assessed actively on each clinic visit by review of study subjects' daily diary cards for potential TEAEs, and oral cavity examination and targeted physical examination, as required.

Metabolic, liver, kidney and hematological laboratory evaluations will be performed at screening and at Day 14 or early termination (and potentially during unscheduled) clinic visits.

Subjects will be instructed to fill out diary cards twice daily to assess their symptoms associated with disease progression and record the number of treatments completed. Each of the eight symptoms will be rated on a 4-point scale from none (0) to severe (3) and a summary severity average will be calculated. Twice daily oral temperatures and oxygen saturation levels (SpO2) will also be recorded on the diary from readings taken by at-home devices dispensed to each subject. Reminders will be sent to each subject twice daily via an appropriate communication platform (e.g. text messaging).

Study Subject safety will be monitored throughout the study by the Investigator and supported by regular review by the Medical Monitor and a Chartered Safety Monitoring Committee.

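### The supportive adjusted Cox model uses baseline severity score and age only as two-group variables, which can pull its hazard ratio towards 1 if either is prognostic

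*SAP*

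**What the plan says.** The primary analysis of each primary endpoint "will be the comparison via an unstratified log-rank test between the RD-X19 treatment arm and sham from the Final Cohort", in the FAS (SAP 5.5.1). A Cox model with treatment alone supplies the main hazard ratio. A second Cox model adds five baseline covariates, "to evaluate the potential impact of subject baseline characteristics to the treatment effect estimation". Two of the five are quantities cut in two:

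- the composite severity score: "severity scores divided by eight (grouping of <1.25" or at least 1.25);
- age: "age (grouping of <50" or at least 50).

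The programming notation confirms that only the grouped form is modelled: "COVIDSEV: grouping of COVID-19 Composite Severity Score at baseline, 1 for score <1.25" and 2 otherwise, with AGEGRP defined in the same way. Code step c) uses these two variables. Protocol 10.4.1 gives the same groupings. Neither document gives a reason for either cut point or plans a version with the values as measured.

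The finer values exist. On the diary, "Each of the eight symptoms will be rated on a 4-point scale from none (0) to severe (3"), and the baseline score is the sum of the eight ratings divided by eight. Eligible subjects are "Males or females, 18 to 65 years of age, inclusive" (Protocol 4.2). SAP Table 14.1.3 already summarises both score and age with means, SDs and ranges.

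**The concern.** The event requires all eight symptoms to fall to none or mild and stay there. The severity covariate is the baseline average of those same eight symptoms, so it is reasonable to expect it to predict the time to resolution. Yet the model treats very different patients alike. Entry needs two moderate symptoms (a score of at least 4/8 = 0.5), or one moderate symptom plus fever or exertional breathlessness (at least 2/8 = 0.25). The lower group can therefore run from 0.25 to 1.125 and the upper from 1.25 to 3.0. Ages 18 and 49 are likewise treated as equal.

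In a Cox model, prognostic variation that is left unmodelled brings the treatment hazard ratio closer to 1. At stake is the adjusted hazard ratio, with its 95% and 90% intervals and p-value, which the SAP tabulates for both primary endpoints in the FAS, mFAS and PP populations.

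**Working it through.** **Inputs from the documents.** Score: eight items rated 0 to 3, so 25 possible values in steps of 1/8 = 0.125; cut at 1.25. Age: 18 to 65; cut at 50. FAS planning case (SAP 3.3): at least 100:50 subjects, hazard ratio 0.5, event proportions 90% and 85%, one-sided 0.025. Counts of 98 mild and 76 moderate, 174 in all (SAP 5.1.1). The code makes sham the reference and the event is resolution, so 0.5 is written below as 1/0.5 = 2.0 in favour of RD-X19.

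**Assumed, because the documents are silent.** Score distribution (mean 1.25, SD 0.4, floor 0.5), uniform age, and prognostic effects that are linear in the log hazard.

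**1. The plan's own figures.** Events = 100 × 0.90 + 50 × 0.85 = 132.5. Schoenfeld power = Φ(|ln HR| × √(events × 2/3 × 1/3) − z) = Φ(0.693 × √29.44 − 1.960) = Φ(1.80) = 96.4%. At the 0.0144 level it is 94.2%. The stated power of at least 90% reproduces. With correlation √(98/174) = 0.750, the Hochberg levels solve to 0.01444 and 0.02970, matching 0.0144 and 0.0297. Both results concern the unadjusted log-rank test, so covariate coding does not enter. No power or precision is stated for the adjusted model.

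**2. Linear information kept by a two-group split.** This is the squared correlation between the variable and its indicator.

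- Normal score with a proportion p below the cut: φ(z_p)² / [p(1 − p)]. At the median this is 2/π = 64%; at a 30/70 split 58%; at 20/80 49%.
- Uniform age: 3p(1 − p). Ages 50 to 65 are 16 of 48 years, so p = 1/3 and 3 × 1/3 × 2/3 = 67%.

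The loss is therefore about 36% for the score at best and about 33% for age.

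**3. Effect on the hazard ratio.** 1,500 simulated trials per row, 116:58 subjects, follow-up to 336 hours, baseline hazard set for 85% sham events, true ratio 2.0. The active-arm event proportion follows from that ratio (1 − 0.15² = 97.8% with no prognostic effect), so it exceeds the SAP's 90%. Entries are the exponentiated mean log hazard ratio. Power is one-sided at 0.025.

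| Score, age effect (log-HR per SD) | Treatment only | Grouped | Continuous | Power, grouped to continuous |
|---|---|---|---|---|
| 0, 0 | 2.00 | 2.01 | 2.01 | 97.8% to 98.0% |
| 0.2, 0 | 1.96 | 2.00 | 2.02 | 98.4% to 98.5% |
| 0.2, 0.2 | 1.93 | 1.99 | 2.02 | 97.8% to 98.1% |
| 0.4, 0.2 | 1.84 | 1.95 | 2.02 | 97.2% to 97.9% |
| 0.6, 0.2 | 1.74 | 1.91 | 2.02 | 95.6% to 97.8% |

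The continuous fit itself sits about 0.02 above 2.0, so the useful comparison is between the two codings on the same simulated data. In the strongest row the grouped ratio is 1.907/2.024 = 0.94 of the continuous one. Even there, the grouped model closes (1.907 − 1.735)/(2.024 − 1.735) = 60% of the gap left by the treatment-only model. At a true ratio of 1.5, the strongest row goes from 1.45 (power 57.3%) to 1.50 (63.7%). With no prognostic effect the power figures there are 64.6% and 66.1%, a gap that reflects simulation noise.

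**4. Precision.** The mean standard error of the log hazard ratio is 0.177 in every grouped row and 0.177 to 0.179 in the continuous rows. In the strongest case the 95% interval width on the log scale is 2 × 1.96 × 0.177 = 0.694 grouped against 2 × 1.96 × 0.179 = 0.702 continuous. The grouped interval is not wider.

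**The case against.** No efficacy decision rests on this model. Protocol 10.1 limits hypothesis testing to the two primary endpoints, the Hochberg rule in SAP 5.1.1 works on their primary analysis, and the significance flags attach only to that log-rank test. Both documents prespecify the same groupings, so the coding is a legitimate choice and not a contradiction. All of this stands, and it makes the power column above descriptive only.

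The size of the effect depends on prognostic strength that neither document reports. The simulation also favours the continuous model: effects were generated as linear, no threshold shape was tried, and disease status, sex and antibody status were left out. In the weak-effect rows the grouped estimate is at least as close to 2.0 as the continuous one. This too stands, so attenuation can be stated only conditionally.

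A reader might go further and infer that the cuts widen the 95% and 90% intervals. Step 4 shows no such loss. A reader might also infer that chance imbalance within the groups has been shown to distort the estimate, but the simulation does not isolate imbalance and no such claim is made here.

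What the objection does not remove is that the finer values are already collected and that no analysis in either document uses them in this model.

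**Conclusion.** The point holds as a minor improvement to a supportive analysis. If score or age predicts time to resolution, the grouped model reports a hazard ratio averaged over the variation left within each group, which lies closer to 1 than the ratio conditional on the values themselves. For a true ratio of 2.0, the gap between the two codings is about 0.02 to 0.03 under weak assumed effects and about 0.12 under the strongest one tried. It is zero if neither variable is prognostic. These sizes rest on the assumed distributions, effect sizes and linearity, and not on trial data.

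It would be tempting to conclude that the cuts weaken the trial's efficacy result. The documents do not support that: the primary test is unadjusted, the Hochberg levels depend only on the mild and moderate counts, and the stated power belongs to the log-rank test.

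**What to change.** Before unblinding:

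- In SAP 5.5.1, replace the grouped score and age with continuous terms in the covariate list, the notation and code step c). Leave disease status, sex and antibody status as they are. For baseline scores with missing items, apply the rule already given in the first footnote of Table 14.1.3.
- Keep the present grouped model as a named sensitivity analysis. Agreement between the two fits also covers the linearity assumption.
- Make the same edit in Protocol 10.4.1 and in the covariate footnotes of Tables 14.2.1.1 to 14.2.1.4, so that the documents continue to agree.

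The cost is wording, two model variables, one extra fit per table and an amendment of one protocol paragraph. Each variable still uses a single model term and no new data are needed. The statistical price is the linearity assumption. If a protocol amendment is not wanted, the minimum is to add the continuous fit to the SAP as a prespecified sensitivity analysis and leave the grouped model where it is.
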